5.2 Stage 1 (UK only) – Dose titration and tolerability & treatment

Stage 1 is a dose titration of carbamazepine in 5mg/kg increments to a preselected maximum dose of 20mg/kg, with review of safety and tolerability in a population of 11 participants from two UK trial sites over a 12 month period (See Table 6). A safety review will be conducted, once the 11th patient has reached the 6 month time point. For a detailed description of the Stage 1 dose titration, see section 8.8. Once a suitable dose is agreed, Stage 1 participants will continue CBZ treatment at this agreed dose until they reach 24 months treatment (See Table 7). There will also be an opportunity to continue CBZ treatment for an additional 12 months for participants who wish to do so. This optional CBZ treatment will be a subject to an additional informed consent at visit 2.5. Their 12/24 month data will be included in the final analysis following Stage 2, subject to IDMC consultation.

5.3 Stage 2 - Treatment

During Stage 1, the additional 29 Stage 2 participants will be recruited and will commence the 6-month observation period in preparation for the start of Stage 2. Stage 2 is a 12-month CBZ treatment stage in a population of 29 participants from multiple trial sites across the UK, and self sponsored trial sites across Europe and Australia(See Table 3. Stage 2 patients will only begin treatment after the Stage 1 safety review is completed and when an agreed safe and tolerable dose has been identified (section 8.8.6). In the case that the dosing regimen remains the same, Stage 1 participants will be included in Stage 2 analysis. In the case that the dosing regimen changes, the IDMC will be consulted about whether inclusion is appropriate. Participants who are in the Stage 2 treatment phase may be on a lower dosing regimen if they are unable to tolerate the maximum dose of 20mg/kg. The titration will need to be recorded in the patient's notes and documented in the trial MACRO database. Clinical judgement alongside clinical assessments will be used to determine if the dose must be lowered.

6 TRIAL SETTING

This is a multicentre international clinical trial. UK trial sites will be sponsored by the Newcastle upon Tyne Hospitals NHS Foundation Trust. However, International trial sites will be sponsored by a local, country specific Sponsor.

The clinical centres have been selected based on:

- Established track record at an international, or at least national level in the diagnosis and management of patients with Genetic Skeletal Diseases (GSDs) including MCDS
- Previous experience within the centre of participation in clinical trials

• Projected ability to recruit patients with MCDS within proposed timescales

All clinical centres are, or have previously been involved in the routine care and follow up of patients with MCDS and are secondary or tertiary care centres. All trial sites have the services needed for MCDS clinical care, including radiology. MCDS is a very rare disease, and in most cases, the diagnosis is reached at the specialised centres following referrals from primary care or other specialist services. A list of the participating countries can be found in section 6.1 below.

When a patient is diagnosed elsewhere, they are usually referred to the selected specialist centres for the follow up of their rare disease. It is expected that most patients involved in the trial will be identified amongst the patients in the care of the specialised centres that have been selected as trial sites. Some patients may be referred to the trial sites by selected Participant Identification Centres (PICs), which are secondary or tertiary centres with expertise in rare diseases who might identify newly diagnosed patients not yet known to the trial sites.

7 ELIGIBILITY CRITERIA

7.1 Inclusion Criteria

- Participants where a pathogenic mutation in the gene encoding the COL10A1 protein has been identified by sequence analysis
- Ambulant at the time of consent/assent, with open epiphyses
- Willing and able to attend for safety monitoring assessments
- Willing and able to adhere to the trial visit schedule and other protocol requirements

- Capable of giving informed consent, or if appropriate, have an acceptable individual capable of giving consent on the participant's behalf (e.g. parent or legal guardian of a child under 16 years of age)
- Written informed consent signed by parent(s)/legal guardian(s) and/or the subject, according to the local regulations
- If female and of childbearing potential, the participant must have a negative pregnancy test [urine beta-human chorionic gonadotropin (β-hCG)] at baseline and agree to regular pregnancy testing throughout the trial
- Sexually active female participants of childbearing potential must practice true abstinence in line with their preferred and usual lifestyle, or use two acceptable effective methods of contraception whilst on treatment and for a period of 28 days after discontinuation: a barrier method such as a condom or occlusive cap (diaphragm or cervical/vault cap) with spermicidal foam/gel/film/cream/suppository and an established non-barrier method such as oral, injected, or implanted hormonal methods (hormonal preparations must contain not less than 50µg oestrogen). Use of some alternative non-hormonal method of contraception should be considered: an intrauterine device or intrauterine system for the entire duration of the treatment period and for a period of 28 days after discontinuation.

7.2 Exclusion Criteria

- Patients who have reached skeletal maturity*
- Patients who have a planned surgery or planned osteotomy (which in the opinion of the Chief Investigator, Principal Investigator and/or the clinical members of the TMG deems the patient unsuitable for the trial)**
- Patients who have had a prior adverse reaction to carbamazepine or similar drugs such as oxcarbazepine, or to any related tricyclic antidepressants.
- Patients known to have atrioventricular block
- Patients who have a history of bone marrow suppression/depression
- Patients who have evidence of chronic hepatic or renal impairment
- Patients who have acute intermittent porphyria
- Patients who have received a monoamine oxidase inhibitor within 14 days of commencing therapy
- Patients who have abnormal blood screening results at the time of treatment initiation will be excluded unless the Investigator believes the abnormality to be non-significant clinically
- Patients of Han Chinese, Thai and other Asian origins who carry the HLA-B*1502 allele

*Skeletal maturity will be assessed as part of the eligibility criteria. Individuals who may reach skeletal maturity before the end of the study should not be included. Patients will be assessed clinically on a case by case basis through discussion of the site PI^a with the CI and/or the clinical members of the TMG during the screening process.

If a participant reaches skeletal maturity during the treatment phase of the trial, they will be asked to continue on the trial for an additional 6 months from the point of skeletal maturity. Patients will stay on their medication and attend study visits, to evaluate if CBZ may have any effect on MCDS patients after they reach skeletal maturity.

**Patients who have planned surgery or planned osteotomy will not automatically be ineligible for the trial. Every potential participant with planned surgery or osteotomy will be assessed clinically on a case by case basis through discussion of the site PI^a, with the CI and/or the clinical members of the TMG during the screening process. NB: Please ensure that patients fulfil the full eligibility criteria prior to enrolling them on to the trial and ensure eligibility is re-assessed after the baseline observation period is complete, and before the participant begins treatment with CBZ. If a patient is deemed unsuitable at the end of the baseline observation period re-assessment time point, further reassessment of eligibility is possible if the Site PI^a and CI are in agreement that the exclusionary results are subject to change. In such cases, eligibility can be re-assessed within a 3 month period. If a patient meets any of the exclusion criteria after the 3 month reassessment period, they will be withdrawn from the study.

Protocol waivers will not be permitted for this trial. Enrolling a patient who does not meet the inclusion/exclusion criteria is considered a protocol waiver and is in breach of Regulation 29 (SI 2004/1031) of the Medicines for Human Use (Clinical Trials) Regulations 2004 and EU Clinical Trial Directive 2001.

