2.4 Definition of outcome measures

2.4.1.1 Primary objectives/endpoints

	Objective	Outcome
Primary	To evaluate efficacy of CBZ for the treatment of children with MCDS who are ambulant but have not yet reached skeletal maturity (open epiphyses)	Alteration from baseline in growth velocity over 12 months
	To determine if the level of efficacy warrants a subsequent formal development programme for CBZ in this indication.	Growth velocity follow-up data at 12 months post treatment initiation

Participants undergo an observational phase (12-18 months for Stage 1 participants; 6 months for Stage 2 participants) prior to starting treatment. Measurements taken include data on height and weight. The same measurements are taken at various time points during the treatment period, allowing an assessment of growth velocity and any change which might be due to treatment.

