4.3.2 Analysis

All patients who have completed the baseline observation period and have received at least one dose of CBZ will be included in the primary analysis.

Height measurements will be displayed graphically by individual indicating measurements taken during baseline and treatment periods.

Height measurement data will be analysed using the STATA commend **xtgee** to estimate the parameters of the regression model in 4.3.1. The parameter β_3 representing the change in growth velocity will be reported together with 95% confidence interval. The Huber/White/sandwich estimator of variance will be used to obtain confidence intervals [in STATA: vce(robust)].

If fitting the growth model in section 4.3.1 is problematic, for example, lack of convergence, then a simplified analysis will be considered.

For subject *i* (*i* = 1,..,*N*), let v_{ik} denote growth velocity (a continuous response variable) measured during the baseline period (*k*=1) and the treatment period (*k*=2). Growth velocity during the baseline period for each participant will be estimated using the first available and last available measurement during the baseline period; the growth velocity during the treatment period will be estimated in a similar manner.

The model for growth velocity is:

$$v_{ik} = \beta_1 + \beta_{2i} + \beta_3 P_k + \varepsilon_{ik},$$

where β_1 , β_{2i} and β_3 are regression parameters to be estimated using simple linear regression. P_k takes the value 0 for baseline period velocities (*k*=1) and 1 for treatment period velocities (*k*=2). As for the previous GEE model, the parameter β_3 represents the change in growth velocity between treatment and baseline periods. The parameter β_3 representing the change in growth velocity will be reported together with 95% confidence interval.

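### Heights taken after growth-plate closure on treatment have no cut-off in the primary growth model, so any child who matures on carbamazepine adds flat growth to the treatment period only

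*Protocol*

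**What the plan says.** **Target population.** The primary objective in SAP 2.4.1.1 concerns "children with MCDS who are ambulant but have not yet reached skeletal maturity (open epiphyses").

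**Entry.** Protocol 7.2 excludes the skeletally mature and adds a forecast: "Individuals who may reach skeletal maturity before the end of the study should not be included". This is judged case by case. The same section requires that "eligibility is re-assessed after the baseline observation period is complete, and before the participant begins treatment with CBZ".

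**Maturity on treatment.** The footnote to Protocol 7.2 then provides for a child who matures on drug: "If a participant reaches skeletal maturity during the treatment phase of the trial, they will be asked to continue on the trial", for 6 further months counted from maturity. It adds: "Patients will stay on their medication and attend study visits". The stated purpose is to see whether carbamazepine has any effect after maturity. Protocol Tables 6, 7 and 9 schedule growth measurements at every three-monthly treatment visit.

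**Primary analysis.** SAP 4.3.2 states: "All patients who have completed the baseline observation period and have received at least one dose of CBZ will be included in the primary analysis". The model in SAP 4.3.1 sets the treatment indicator to 1 for every treatment-period height and fits one common change in slope, β3. The fallback takes each child's velocity from the first and last available height in each period.

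**Other analyses.** SAP 4.3.3 adjusts for surgery and vitamin D. SAP 4.3.4 restricts by prescribed dose. None mentions maturity.

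**The concern.** The objective is limited to open growth plates because that is where a growth effect can be seen. The retention rule serves a different question, yet the heights it produces enter the primary model on the same footing as all others. A child recorded as mature by the end of baseline should fail the re-check and receive no drug. Recorded closed-plate time therefore has no counterpart in the baseline slope.

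At stake is the primary efficacy estimate, which informs whether a development programme is warranted. Post-closure heights could understate a real gain or produce an apparent loss, and the estimate would then describe a population wider than the one in the objective. The SAP anticipates other influences on growth but not the one event that the protocol itself foresees.

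**Working it through.** There is no planned effect size, SD or power to reproduce; Protocol 11.3 sets N = 40 (11 + 29) by feasibility. The check asks how far β3 moves when closed-plate heights are kept.

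**Inputs from the documents**
- Stage 1: 11 children, heights at 0, 6 and 12 months of baseline, then three-monthly to 24 months of treatment.
- Stage 2: 29 children, heights at 0 and 6 months of baseline, then three-monthly to 12 months.
- Follow-up of 6 months after maturity.
- The SAP 4.3.1 model with exchangeable working correlation ρ.

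**Assumptions not in the documents**
- Growth v of 1-5 cm/yr up to closure and 0 after. The lower end allows for growth that had already slowed.
- ρ of 0.95-0.99. The results barely change within this range.
- Closure at treatment month 18 (Stage 1) or month 6 (Stage 2), so that the 6 extra months end at the last planned visit.

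**GEE.** Let each row of Xᵢ be (1, tᵢⱼ, τᵢⱼ(tᵢⱼ − Tᵢ)), and let mᵢ be the time of closure. Closure lowers a maturing child's heights by dᵢⱼ = −v·max(0, tᵢⱼ − mᵢ). The shift in β3 is the third element of

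(Σ Xᵢ′Rᵢ⁻¹Xᵢ)⁻¹ Σ Xᵢ′Rᵢ⁻¹dᵢ.

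The shift is proportional to v and does not depend on the true drug effect.

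**Fallback.** With one term per child, β3 is the mean within-child change in velocity. A maturing child contributes −v × (6 months ÷ treatment months), averaged over 40 children:
- One Stage 1 child: −v × (6/24)/40 = −0.00625v
- One Stage 2 child: −v × (6/12)/40 = −0.0125v
- Two of each: −v × (2 × 0.25 + 2 × 0.5)/40 = −0.0375v

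| Children maturing | GEE shift per 1 cm/yr | GEE, v = 1-2 | GEE, v = 3-5 | Fallback, v = 1-5 |
|---|---|---|---|---|
| None | 0 | 0 | 0 | 0 |
| One Stage 1 | −0.0185 | −0.02 to −0.04 | −0.06 to −0.09 | −0.006 to −0.03 |
| One Stage 2 | −0.0070 | −0.007 to −0.014 | −0.02 to −0.035 | −0.01 to −0.06 |
| Two of each | −0.0509 | −0.05 to −0.10 | −0.15 to −0.25 | −0.04 to −0.19 |

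All shifts are in cm/yr.

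**Direction.** In the fallback the shift is negative whenever a child matures. In the GEE it is negative in every row above. The same formula gives a small positive shift if a Stage 1 child closes in the first months of treatment: +0.007 per 1 cm/yr at month 3, and close to 0 at month 6. Those early flat heights also pull down the common slope β2.

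**Against sampling error.** The GEE was also simulated on the planned visits. The assumptions were growth of 4-6 cm/yr, a drug effect of +1 cm/yr, a between-child velocity SD of 0.8 cm/yr and a measurement SD of 0.3 cm. The standard error was about 0.13-0.22 cm/yr. Keeping the heights of three maturing children shifted β3 by −0.08 to −0.22, and of four by −0.14 to −0.32. With no drug effect at 5 cm/yr, three such children gave β3 of −0.19 with their heights kept and −0.03 with them dropped.

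**The case against.** **Screening should make this rare.** The forecast rule in Protocol 7.2, the re-check before drug and a further check before the optional extension all work to keep maturing children out. This stands as a limit on size: nothing in the documents supports any particular number, and four of 40 is only an illustration. It does not remove the gap, because the forecast is a clinical judgement and the next paragraph provides for it being wrong. For Stage 1 the horizon can also be long: baseline of up to 18 months plus up to 36 months of treatment.

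**The effect of one child is small.** This stands. One child moves β3 by well under one simulated standard error, and by less still if growth had already slowed. About three or more are needed to approach one.

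**Protocol 8.8.7 takes the Stage 1 endpoint at the end of dose titration.** Under that reading, Stage 1 heights at months 18-24 would not count. The SAP model sets no such limit, so the Stage 1 figures apply to the SAP as written.

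**An all-treated analysis is defensible.** Open epiphyses is an entry criterion, and stopping at closure conditions on something that the drug might influence. If carbamazepine hastened closure, the cut would hide that loss. This stands, and it is the reason to add the cut analysis rather than replace the all-treated one.

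**Conclusion.** The gap is real and conditional. The plan foresees children who mature on treatment, keeps measuring them, and has no rule for their heights in a primary model whose objective excludes mature children. That the heights stay in follows from the all-treated rule and the SAP's silence, not from an explicit instruction.

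The size depends on the unknown number of children, on v and on the timing of closure. It runs from nil, through a few hundredths of a cm/yr for one child, to −0.05 to −0.25 cm/yr for two from each stage. Zero growth after closure is an assumption, although it fits the documents' reason for enrolling immature children.

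A reader might infer more than the documents support:
- *That the trial's result is biased.* No count of maturing children is given.
- *That β3 must fall in every case.* That is exact for the fallback. For the GEE it holds in the scenarios tabulated, but not for closure very early in treatment.
- *That the net bias is downward.* The argument covers this mechanism only, not every bias of an uncontrolled before-after comparison.
- *That β3 is the only efficacy estimate.* It is the primary one; SAP 4.4.2 also models height z-score, pain and quality of life.
- *That post-maturity visits have no other use.* SAP 4.3.2 and 4.4.1 plot data by individual. What is missing is any labelled or separate analysis of those visits.

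**What to change.** Before the final analysis, add to SAP 4.3.4, and apply to the fallback, a pre-specified analysis of β3 that uses each child's heights only up to the last visit before epiphyseal closure is documented. Date closure from the scheduled left-wrist X-rays, and state in the SAP which reading counts as closure. Protocol Tables 5-9 list no site-recorded date of maturity, so the rule should not depend on one.

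Report this beside the all-treated result, summarise post-maturity heights separately by child (the question for which Protocol 7.2 keeps them), and state how many children and visits are affected. If the count is zero, saying so closes the matter.

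The cost is SAP wording and one derived date from films already planned. A few late heights are lost from the added analysis, and closure is dated only to within the 6-12 month X-ray interval. The cut would also hide any effect of the drug on closure itself, so neither result should be shown without the other.

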8 TRIAL PROCEDURES

8.1 Recruitment

8.1.1 Patient Identification

Participants will be recruited from the existing MCDS patient populations or newly diagnosed patients in the clinical centres involved in the trial. All clinical centres are regional or national referral centres for the diagnosis and management of patients with GSDs including MCDS.

Potential participants and their parent(s)/legal guardian(s) will be provided with trial information in the form of a Participant Information Sheet (PIS) given either via an invitation letter sent through the post or a copy of the PIS provided during a patient's routine clinic appointment.

As the trial will be recruiting from a paediatric population, age appropriate documentation will be used.

8.1.2 Participant Identification centres (PICs)

Due to the rare nature of the MCDS condition, some of the trial centres may use Participant Identification Centres to identify participants. The PICs will identify potential participants from existing MCDS patient populations or newly diagnosed patients based on trial eligibility criteria. The trial will be discussed with potentially eligible patients and their parent(s)/legal guardian(s) and a copy of the participant information sheet provided. If a potential participant is interested in taking part in the trial, they will be referred to the nearest or most appropriate trial site and will be contacted by the local trial team by their preferred method of contact.

8.2 Consent/Assent

Following provision of trial information, participants and their parent(s)/legal guardian(s) will be invited to attend a consent/assent visit with their local trial team, having been given a minimum of 24 hours to consider the information provided. At the visit, the trial will be explained and discussed with the patient, allowing sufficient time to go through the details of the trial and for the clinician to answer any questions the patient and their parent(s)/legal guardian(s) might have.

The consent/assent process will include sufficient time to discuss the aim of the trial, trial procedures and the commitment required from the family and the patient. It will also include sufficient time for patients and their parent(s)/legal guardian(s) to ask all questions they might have and clarify any doubts. Only after their questions and concerns have been adequately addressed will informed

consent/assent be sought. The patient will be given the opportunity to discuss any aspect of the trial, including risks of pregnancy and contraception, without their parent(s)/legal guardian(s) present if required.

If the patients and parent(s)/legal guardian(s) agree to take part in the trial, they will be asked to sign and initial consent and assent forms, which will be also signed by the member of the trial team delegated by the Principal Investigator (PI^a)to perform this task. Informed consent/ assent will only be sought by a member of the trial team who is medically qualified, appropriately trained and delegated to do so. Consent/assent will be obtained prior to trial screening. N.B Informed consent is ongoing process, if a participant moves age groups during the trial, the age appropriate PIS will be provided, and the participant will be re-consented.

The age requirements for parental consent for children's participation in research differs between EU Member States.

For UK based participants, consent will be sought from patients who are 16 and over and the parent(s)/legal guardian(s) of patients under the age of 16. Furthermore, assent will be taken from patients aged between 7-15 years. For non-UK based participants, local regulations concerning ethics approval and informed consent will be followed for defining the age ranges for subjects capable and not capable of giving written assent. Subjects will be re-consented with the appropriate age-related documents as needed, if required by local regulations.

For the purposes of the MCDS-Therapy trial, consent, assent and patient information documentation will be translated into the relevant languages of the participating European sites where required.

The original signed consent and assent forms will be retained in the Investigator Site File (ISF), with copies provided to the patient/parent(s)/legal guardian(s), a copy filed in the patients' clinical notes and a copy sent by secure methods to Newcastle Clinical Trials Unit (NCTU) (UK centres only). The copy sent to NCTU for monitoring purposes will be destroyed once reviewed. Following consent/assent, the site will allocate the participant their unique trial identification number. The unique trial ID number will be made up of a 2-digit site code and a 3-digit patient code, starting with 001 for the first patient at that site and continuing sequentially with each consenting patient (Table 3).

Site	Site code
The Newcastle upon Tyne Hospitals NHS Foundation Trust,	10
Newcastle upon Tyne UK (NuTH)	
Guy's and St. Thomas' Hospital, London UK (GSTFT)	11
Rizzoli Orthopaedic Institute, Bologna Italy (IOR)	12
University of Freiburg- Freiburg Germany (UKL-FR)	13
Assistance Publique – Hôpitaux de Paris – Paris France (AP-HP)	14
Murdoch Children Research Institute, Melbourne Australia (MCRI)	15
University of Antwerp, Antwerp Belgium (UZA)	16

Table 3 – Site unique trial ID numbers

